Although considered a modifiable risk factor for coronary artery disease (CAD) in the general population, the magnitude of physical activity required to promote cardiorespiratory fitness and a clinically meaningful change in blood-derived biomarkers of CAD is not achievable in those with a severe physical disability, such as with immobilizing paralysis from spinal cord injury (SCI). During the chronic phase of SCI, a characteristic dyslipidemia emerges, with mean serum high density lipoprotein cholesterol (HDL-C) concentrations <40 mg/dl, a threshold level for HDL-C that is appreciated to be an independent risk factor for CAD, elevations in triglycerides (TG) to concentrations at, or near, target values for the general population that trigger clinical intervention, and low density lipoprotein cholesterol (LDL-C) concentrations that are within the normal range. It should not be a surprise that cardiovascular disease (CVD)-related morbidity in persons with SCI occurs earlier in life, at a greater prevalence than that of the general population, and is the primary cause of death after the first year of injury. Population-based epidemiological studies are unavailable for clinical guidance because of the relatively low incidence rates for SCI. Clinical target values used to initiate treatment in the general population may be inappropriate in those with SCI because of their unique pathophysiology. In the absence of significant physical activity and lifestyle modifications, it would seem that appropriate pharmaceutical options are needed to properly manage markers of CVD-related risk in persons with SCI. To date, there is limited empirical evidence to support the use of lipid-lowering treatments in persons with SCI.

Fenofibrate is a fibric acid derivate that activates peroxisome proliferator-activated receptor α and lipoprotein lipase, leading to enhanced elimination of TG from plasma. In clinical trials where fenofibrate was used as a monotherapy, serum TG concentrations fell 41-53%, very low-density lipoprotein (VLDL) fell 38-52%, LDL-C decreased 6-20%, and HDL-C improved by as much as 20%. In consideration for the nature of dyslipidemia in persons with

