SCI, fenofibrate appears to be an appropriate first-line agent for treatment in this cohort, especially because most of those with SCI have LDL values that are within the clinically acceptable range. In the general population, standard clinical practice for lipid-lowering treatment with fenofibrate monotherapy follows a known and clinically accepted timeline to monitor safety and to determine therapeutic efficacy. It is recommended that, if after 2 months of continuous therapy there are no beneficial changes to the lipoprotein profile, that treatment be discontinued (i.e., non-responders). Similarly, several large clinical trials have demonstrated that the peak therapeutic effects of fenofibrate are observed after 12-16 weeks of treatment (i.e., responders). The proposed study will test the efficacy of administering fenofibrate to persons with SCI, a severely immobilized cohort that does not have established clinical practice guidelines to treat dyslipidemia and appears to have unique considerations that may be hypothesized to call for a more disease-specific approach for care. If successful, the treatment will reduce clinical markers of CVD-related risk by modifying the concentration and number of particles that are known to contribute to incident cardiac events and mortality. It is anticipated that the insight gained from this investigation will provide clinicians with a proof-of-concept for instituting appropriate use of lipid lowering agents to treat the dyslipidemia that has been well described in persons with SCI.

Goals and Objectives

In individuals with spinal cord injury (SCI):

Primary Aim:

1. To determine the efficacy of fenofibrate monotherapy after 2 months of treatment to improve the lipoprotein profile; a successful response will be defined as a 25% reduction in the serum TG concentration at 2 months. This approach will permit the determination of the percent of subjects who show drug efficacy (i.e., responders) versus those who are non-responders after 2 months of treatment, when drug administration will be discontinued if therapeutic efficacy is deemed suboptimal.
2. To determine the efficacy of fenofibrate monotherapy to lower TG concentration at 4 months of treatment, when the peak therapeutic efficacy to drug treatment has been reported to occur. Lipid profiles will be performed in the drug responder and control groups.

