The proposed investigation is an open-label, parallel-group intervention and randomized trial to determine the safety and efficacy of fenofibrate monotherapy on the lipoprotein profile in persons with SCI. A screening visit will be performed in up to 100 persons with SCI to identify 30 subjects who have adverse TG concentrations (i.e., paraplegia: ≥ 135 mg/dl; tetraplegia ≥ 115 mg/dl). After a baseline evaluation, a comprehensive medical history review and intake interview will be performed to identify demographic information, current health status, medications and lifestyle habits (i.e., smoking, alcohol consumption, recreational drug use, physical activity habits, diet etc.). Twenty subjects with adverse TG concentrations will be randomized to receive once daily fenofibrate therapy (i.e., 145 mg) for 4 months (dispensed by the research pharmacy of the James J. Peters VA Medical Center) and the remaining 10 subjects with adverse TG concentrations will receive no treatment and will serve as control subjects. All subjects will complete monthly follow-up visits for the study period, which also includes a 1-month post-treatment visit. If after 2 months of continuous fenofibrate treatment a subject does not demonstrate an improvement of $\geq 25\%$ in TG concentration, then he/she will be discontinued from the study drug under appropriate supervision and terminated from the study. For those who respond to fenofibrate treatment, he/she will continue on treatment for an additional 2 months.

The primary study outcome will be to determine the efficacy of treatment on the serum lipoprotein profile (i.e., TG, HDL-C, LDL-C, total cholesterol), and the secondary study

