outcome will be the lipoprotein particle number and size by NMR (i.e., HDL, LDL and VLDL subfractions). Liver (enzymes: AST, ALT, GGT) and kidney function (i.e., glomerular filtration rate) tests, and a complete blood count (CBC) with differential will be performed at all study visits, from blood samples, respectively, to monitor subject safety (Table 2). To facilitate our understanding of the relationship between metabolic parameters, body composition and primary study outcome measurements associated with treatment efficacy, a 2 hour oral glucose tolerance test, and a total body dual energy x-ray absorptiometry (DXA) scan will be performed to quantify total body fat mass and fat-free mass at baseline, as well as to determine visceral adipose tissue volume (enCore™ software (Lunar iDXA, platform version 13.6, General Electric Medical Systems, Madison, WI) at baseline and at 4 months. In addition, all subjects who enter the trial as a treatment or control subject will receive dietetic counseling at baseline and at 2 months. Study support staff will perform phone calls twice a month to monitor drug compliance and direct concerns to the study physician during intervals when there may be noncompliance with scheduled study follow-up visits. Thus, the proposed research investigation incorporates and follows best practices for the clinical treatment and utility of fenofibrate monotherapy in persons with dyslipidemia.

Table 2. Table of Procedures

	Screening	Baseline	Treatment				Follow-Up
			Month 1	Month 2	Month 3	Month 4	Post- 1 month
Safety Labs							
Liver and Kidney Function	x	x	x	x	x	x	x
CBC with Differential	x	x	x	x	x	x	x
Primary Study Outcomes							
Lipoprotein Concentrations	x	x	x	x	x	x	x
Lipoprotein Particle Number		x	x	x	x	x	x
Additional Outcomes							
Fasting Insulin, Glucose and A1	x	x	x	x	x	x	x
Oral Glucose Tolerance Test		x				x	
Body Composition Analysis		x				x	
ApoE blood genotyping		x					

Procedures

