Separate analysis of variance (ANOVA) will be performed to identify group differences (i.e., control, treatment) for baseline demographic data [e.g., age, height, weight, BMI, duration of injury (DOI)]. Pearson chi-square tests will be performed to identify differences for the number of enrolled participants in each group based on gender (e.g., male, female), injury level (e.g., paraplegia, tetraplegia), AIS level (e.g., A, B, C), and ethnicity (e.g., African American, White, Hispanic). Separate 2 (group: treatment, control) X 3 (visit: baseline, Mo2, Mo4) mixed-model repeated measures ANOVA (RMANOVA) will be performed to determine if differences were present for serum lipoprotein profile [e.g., HDL-C, LDL-C, VLDL-C, TG, TC], glucose, insulin, and the TG/HDL-C, LDL-C/HDL-C and TC/HDL-C ratios. Separate

factorial ANOVA will be performed to identify the presence of group differences in the percent change from baseline to 2 and 4 months, respectively in the serum TG, HDL-C, and LDL-C. The nature of significant group or time main effects will be explored with Tukey *post hoc* tests. Although not part of the primary analysis, results from the venous blood samples at months 1 and 3 visits will be provided. Statistical analyses will be completed using IBM SPSS Statistics 25 (IBM, Armonk, NY) and figures will be created with GraphPad Prism (version 8.0 for Windows, GraphPad Software, San Diego, CA). An *a priori* level of significance was set at $p \leq 0.05$.

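### The month-4 percent-change test sets drug responders, selected on TG after randomisation, against unselected controls, which biases it toward fenofibrate if the 25% cut is taken from baseline

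*Combined protocol and SAP*

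**What the plan says.** Goals and Objectives, Primary Aim 1, sets the response rule: "a successful response will be defined as a 25% reduction in the serum TG concentration at 2 months". Methods applies it to the drug arm only. A treated participant who misses the cut "he/she will be discontinued from the study drug under appropriate supervision and terminated from the study", while responders stay on drug for two more months. No matching rule exists for the 10 controls. The same paragraph of Methods also says that every subject attends monthly visits through the post-treatment visit, which does not fit with termination at month 2.

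Primary Aim 2 is "To determine the efficacy of fenofibrate monotherapy to lower TG concentration at 4 months of treatment", and its data source follows: "Lipid profiles will be performed in the drug responder and control groups".

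Statistical Analyses plans two group comparisons that involve month 4:

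- A "2 (group: treatment, control) X 3 (visit: baseline, Mo2, Mo4) mixed-model repeated measures ANOVA (RMANOVA") on TG and the other lipids.
- For TG, HDL-C and LDL-C, a "factorial ANOVA will be performed to identify the presence of group differences in the percent change from baseline to 2 and 4 months".

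No analysis set is named for either, and nothing is said about participants with no month-4 visit. The documents also do not say which pre-treatment reading the 25% refers to. The "Lipoprotein Concentrations" row of Table 2 has a draw at both screening and baseline.

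**The concern.** At month 4 the drug arm contains only participants who passed a test on the outcome variable after randomisation. The control arm contains everyone, so randomisation no longer protects the comparison.

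Percent change makes this worse. If the cut is taken from baseline, percent change at month 2 and at month 4 have the same denominator. A participant whose baseline was high by chance is more likely to pass at month 2, and then shows a fall at month 4 for the same reason, whatever the drug does.

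Primary Aim 2 is the plan's assessment of peak efficacy. Followed as written, its percent-change result mixes drug effect with selection. The mixture is smallest when nearly everyone responds and largest when the effect in SCI is modest or absent, which is what the trial is meant to find out.

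**Working it through.** **Inputs from the documents.** 20 treated and 10 controls (Target Population, Methods); 25% cut at month 2 (Goals and Objectives, Methods); significance level 0.05 (Statistical Analyses); and, from monotherapy trials cited in the Scientific Abstract, "serum TG concentrations fell 41-53" per cent. The plan gives no SD, power calculation or expected month-4 difference, so it has no figure of its own to reproduce.

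**Assumptions, not in the documents.** TG is log-normal. Visit-to-visit log SD within a person, σ, is 0.20 or 0.30, independent across visits. Every treated participant has the same fall f at months 2 and 4. The 25% is measured from the baseline visit. There is no other dropout. Between-person variation cancels out of percent change.

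**Step 1: the link.** Let e0, e2 and e4 be the visit errors on the log scale. A treated participant is retained if e2 − e0 ≤ c, where c = ln(0.75/(1 − f)). The month-4 log ratio contains e4 − e0. Each difference has variance 2σ² and they share e0, so their covariance is σ² and their correlation 0.5.

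**Step 2: who passes by chance.** P(retained) = Φ(c/(σ√2)). With f = 0, c = −0.2877.

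- σ = 0.20: Φ(−1.017) = 0.155, or 3.1 of 20.
- σ = 0.30: Φ(−0.678) = 0.249, or 5.0 of 20.

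**Step 3: mean month-4 ratio to baseline.**

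- Controls: exp(σ²).
- All treated: (1 − f)·exp(σ²).
- Responders: (1 − f)·exp(σ²)·Φ((c − σ²)/(σ√2)) / Φ(c/(σ√2)).

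With f = 0 and σ = 0.20, responders are at 1.0408 × 0.798 = 0.831 (−16.9%) and controls at +4.1%, a gap of −21.0 points. With σ = 0.30, responders are at 1.0942 × 0.750 = 0.821 (−17.9%) and controls at +9.4%, a gap of −27.3 points. The true gap is 0 in both.

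**Step 4: with a drug effect.** Each cell gives σ = 0.20, then σ = 0.30. Inflation is all treated minus responders, from unrounded values.

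| True fall | Retained of 20 | All treated, % change | Responders, % change | Inflation, points |
|---|---|---|---|---|
| 0% | 3.1; 5.0 | +4.1; +9.4 | −16.9; −17.9 | 21.0; 27.3 |
| 20% | 8.2; 8.8 | −16.7; −12.5 | −27.7; −28.7 | 11.0; 16.3 |
| 30% | 11.9; 11.3 | −27.1; −23.4 | −33.9; −34.8 | 6.8; 11.4 |
| 41% | 16.0; 14.3 | −38.6; −35.4 | −41.8; −42.3 | 3.2; 6.9 |
| 53% | 19.0; 17.3 | −51.1; −48.6 | −51.9; −51.6 | 0.8; 3.1 |

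**Step 5: the test.** In simulated trials with no drug effect and at least two responders, the month-4 percent-change test rejects in about 13 to 15%. With all 30 participants followed and analysed it rejects in about 5%.

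**Step 6: where the bias stops.**

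- If screening is the reference reading, the cut and the month-4 percent change share no visit. The covariance in Step 1 is 0 and the bias vanishes under a common effect.
- Month-4 TG level, taken without baseline, does not involve e0 or e2, so it is unbiased under a common effect. It is biased if individual response varies. With an assumed response log SD of 0.2, a true 20% fall reads as 26 to 28%.

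**Step 7: the repeated-measures ANOVA.** Fitted by likelihood to all available visits, with the same effect in everyone, its month-4 error is 0 to 1.5% of the control mean across true falls of 0 to 53%; with varying response it is 1 to 10%. If participants without month 4 are dropped, the treated baseline and month-2 cells are selected too. The label mixed-model does not settle which is meant.

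**The case against.** Several points can be made for the plan.

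**Statistical Analyses never mentions responders.** True, but the month-4 set follows from Methods and Primary Aim 2 together: terminated participants have no month-4 value.

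**Percent change is not the only month-4 analysis.** This stands. A reader might infer that every month-4 comparison overstates the drug effect, but the documents do not support that. Aim 2 speaks of concentration, and the repeated-measures ANOVA covers TG at month 4. A likelihood fit to all visits would be largely protected. The bias shown here belongs to the percent-change contrast; for the repeated-measures ANOVA the defect is an unstated rule.

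**Month 2.** A reader might also infer that the month-2 comparison is biased. Nothing proposes limiting it to participants who reach month 4. Aim 1 counts responders against non-responders at that visit, and the Secondary Aim studies both groups there. What is missing is a named analysis set.

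**The responder fraction would expose an inactive drug.** Largely so. In simulations with no effect, a month-4 rejection alongside at least 10 of 20 responders occurred in 0.01 to 0.4% of trials. That limits the harm at the null. It does not correct the size of the effect at a 20 to 30% fall, where about half the arm is retained.

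**The expected effect is large.** At falls of 41 to 53% the inflation is only 1 to 7 points. Those figures are background from other trials, however, and the Scientific Abstract itself says that evidence for lipid-lowering treatment in SCI is limited.

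**Conclusion.** The point holds for the month-4 percent-change test of responders against controls. Followed as written, with the 25% measured from baseline, that test is biased toward the drug. I am confident of the direction under that reading.

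The sizes rest on the assumed within-person SDs and a common effect: a false gap of about 21 to 27 points with no effect, and inflation of about 11 to 16, 7 to 11, 3 to 7 and 1 to 3 points at true falls of 20, 30, 41 and 53%. If the reference is the screening reading, the percent-change bias disappears under a common effect and remains only through varying response.

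Whether the repeated-measures ANOVA is affected cannot be settled from the plan, because its handling of a missing month 4 is not stated. None of this is a criticism of the rule for stopping drug. The finding concerns what is compared and how it is labelled.

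**What to change.** 1. Do not use the month-4 percent-change test of responders against controls as evidence of efficacy. Report responders' month-4 percent change descriptively, labelled as conditional on month-2 response, with the number retained out of 20. The month-4 HDL-C and LDL-C percent changes come from the same selected group and should carry the same label; the size of any bias in them was not checked.

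2. Rest the between-group efficacy conclusion on all 30 randomised participants: the month-2 percent-change comparison with that analysis set named, and the 2 × 3 repeated-measures analysis specified as a likelihood-based mixed model. The model should keep every baseline and month-2 value and drop no one for a missing month 4. State that its month-4 term assumes data missing at random, estimates an on-drug effect for non-responders who were not observed then, and may be unstable with few responders. With no drug effect, 41 to 82% of simulated trials had fewer than five.

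3. Reconcile the two statements in Methods, that all subjects attend monthly visits and that non-responders are terminated. State which pre-treatment reading the 25% refers to. No clinical rule is proposed.

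The cost is mostly wording, but it touches a stated objective: Aim 2's month-4 percent-change claim becomes descriptive. Month-4 estimates will be wider and less favourable. How Methods is reconciled could change which visits terminated participants attend.

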Secondary Aim: To describe the effects of fenofibrate monotherapy on lipoprotein particle number and size by nuclear magnetic resonance spectroscopy performed in non-responders and responders at 2 months of treatment, when drug treatment will be discontinued for lack of efficacy to agent. Lipids in responders and control groups will be studied by NMR spectroscopy at 4 months of treatment, which will be at the termination of the proposed treatment period.

Tertiary Aim: To determine the safety of fenofibrate monotherapy. Documentation and description of adverse events will be obtained in subjects who have received drug treatment compared to events occurring in the control group.

Target Population

It is estimated that approximately 100 participants with SCI will be screened to identify 30 eligible and appropriate SCI participants (i.e., 20 treatment, 10 control) who will agree to participate in the study (Screening data from BAU-11-075 will be used to minimize the number of procedures performed, if it is not older than 45 days). To be considered eligible for the study, participants must meet the following eligibility criteria:

Inclusion Criteria:

- (1) Male or female, age 21 to 69;
- (2) Chronic (e.g., duration of injury at least 6 months), stable SCI (regardless of level of neurological lesion);
- (3) American Spinal Injury Association Impairment Scale (AIS) designation of A, B or C; and
- (4) TG concentration ≥ 135 mg/dl (paraplegia) or ≥ 115 mg/dl (tetraplegia).

Exclusion Criteria (These exclusion criteria were carefully chosen to minimize subject risk and/or confounding factors that are known to affect study endpoints):

- (1) Acute illness or infection;
- (2) Reduced kidney function (by glomerular filtration rate (GFR < 60 ml/min) or liver function tests (LFTs ≥ 2.5 times above the upper limit of normal) as determined by test results at screening and any time point of the study;
- (3) Current pharmacological treatment with: HMG-CoA reductase inhibitors (statins), or any other hypolipidemic agent; anti-coagulant therapy; cyclosporine; or any other medications known to effect the TG concentration (i.e., β -blockers, thiazides or estrogen);
- (4) Hypersensitivity to fenofibrate;
- (5) Existing diagnosis of atherosclerosis, congestive heart failure, or recent history of myocardial infarction (i.e., ≤ 12 months);
- (6) Pregnancy or women who may become pregnant during the course of the study, or those who are nursing;

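### TG, on which both primary aims turn, is not carried into Methods or Statistical Analyses as the deciding test, and the responder percentage has no between-arm comparison

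*Combined protocol and SAP*

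**What the plan says.** **Goals and Objectives.** Primary Aim 1 is "To determine the efficacy of fenofibrate monotherapy after 2 months of treatment to improve the lipoprotein profile", but its criterion is TG only: "a successful response will be defined as a 25% reduction in the serum TG concentration at 2 months". It adds: "This approach will permit the determination of the percent of subjects who show drug efficacy". Primary Aim 2 is "To determine the efficacy of fenofibrate monotherapy to lower TG concentration at 4 months of treatment".

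**Methods.** "The primary study outcome will be to determine the efficacy of treatment on the serum lipoprotein profile (i.e., TG, HDL-C, LDL-C, total cholesterol"). The four lipids are not ranked. A treated participant whose TG has not improved by at least 25% after 2 months leaves: "he/she will be discontinued from the study drug under appropriate supervision and terminated from the study".

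**Statistical Analyses.**
- Each lipid has its own 2 (group) × 3 (baseline, month 2, month 4) repeated-measures ANOVA. So do glucose, insulin and three ratios.
- TG, HDL-C and LDL-C are tested again as percent change from baseline to months 2 and 4, by a factorial ANOVA whose factors are not listed. Total cholesterol has no percent-change test.
- Months 1 and 3 are placed outside the primary analysis.
- Significant group or time main effects are followed up with Tukey tests. The single threshold is p ≤ 0.05.
- The only tests of proportions are chi-square tests on enrolment characteristics. The responder percentage has no analysis.

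**The concern.** The aims point to one lipid, Methods makes four jointly primary, and the analysis section does not settle which decides. It ranks neither month 2 nor month 4 and does not say which of the two TG analyses governs. Tukey tests adjust among levels within one model, not across lipids. An efficacy conclusion could therefore rest on HDL-C or LDL-C when TG shows nothing, and nothing in the plan would rule that out.

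The 25% rule does not close the gap, because it classifies individuals and is not a trial-level test. The treated-arm percentage also cannot be read as drug efficacy alone. TG varies within a person, entry requires TG above a threshold, and both arms receive dietetic counselling at baseline. Each could produce 25% falls without the drug, and only the control-arm percentage shows how many.

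**Working it through.** The documents give no power, effect size, SD or error rate across outcomes, so there is no stated figure to reproduce.

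**Inputs from the documents.** 20 treatment and 10 control; threshold 0.05; response = TG fall ≥25% at month 2; percent-change tests for TG, HDL-C and LDL-C; published TG falls with fenofibrate of 41-53% (Scientific Abstract).

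**Assumptions (not in the documents).** Lognormal lipids with log-SD 0.35 (TG), 0.20 (HDL-C) and 0.25 (LDL-C). Within-person correlation r between visits of 0.6 or 0.75. Between-lipid correlations from zero to strong (TG-HDL-C 0 to −0.8; TG-LDL-C 0 to 0.8; HDL-C-LDL-C 0 to −0.6), in seven combinations. No drug effect.

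**1. False favourable result at month 2.** Pooled two-sided t-tests (28 df) on percent change, 40,000 simulated trials per combination. Favourable means TG down, HDL-C up or LDL-C down.

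| Quantity | Range |
|---|---|
| TG favourable | 2.7-2.8% |
| TG, HDL-C or LDL-C favourable | 5.5-7.6% |
| HDL-C or LDL-C favourable, TG not | 2.7-4.8% |
| Third row as a share of the second | 49-64% |

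Hand check: three independent tests at 2.5% in the favourable direction give 1 − 0.975³ = 7.3%. That is near the top of the range, and correlation lowers it. A repeat with a different random seed agreed to within about 0.3 percentage points on the three rates and about 2 points on the share.

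The repeated-measures ANOVAs and total cholesterol are not in these figures.

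**2. Chance of a 25% TG fall with no drug effect.** The log change has SD 0.35 × √(2(1 − r)), and the required change is ln 0.75 = −0.288.
- r = 0.6: SD 0.313; z = −0.288/0.313 = −0.92; probability 17.9%.
- r = 0.75: SD 0.247; z = −0.288/0.247 = −1.16; probability 12.3%.

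Among 20 treated: 20 × 0.123 = 2.5 to 20 × 0.179 = 3.6, or about 2-4 apparent responders.

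**3. Power of a single month-2 TG test.** Noncentrality = (difference/SD) × √(20 × 10/30) = (difference/SD) × 2.582; 28 df; two-sided 0.05. The SD of percent change is assumed to be 25-35 points; the simulation in step 1 gives 25.9-33.7.

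| Arm difference | SD 25 | SD 30 | SD 35 |
|---|---|---|---|
| 25 points | 70% | 55% | 43% |
| 41 points | 98% | 93% | 83% |

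**4. Precision of the responder difference.** Newcombe 95% CI, illustrative counts: 12/20 v 1/10 gives 50 points (13 to 70); 10/20 v 2/10 gives 30 points (−7 to 55).

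**The case against.** The best defence is that TG is plainly the lead lipid. Both aims, the entry criterion and the continuation rule use it, and Statistical Analyses tests TG percent change at exactly the two months the aims name. In a small open-label study presented as proof of concept, formal control across lipids may seem excessive, and the month-2 inflation is modest.

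Much of this stands. A reader might infer that the plan has no lead lipid or visit at all; the aims do name TG at months 2 and 4. A reader might also infer that success on any one lipid is declared sufficient; no section says so. What is missing is the sentence that carries TG forward and ranks the months, and Methods points the other way by listing four lipids as primary.

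Larger error rates are tempting, such as 1 − 0.95⁴ = 18.5% for four lipids. That figure assumes independence and counts significant worsening, which could not support an efficacy claim. Pooling months 2 and 4 is no better: treated non-responders leave after month 2, so month-4 error is largely a matter of selection, a separate problem that ranking lipids does not cure.

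Table 2 and Procedures place NMR particle measures under a primary heading, although the Secondary Aim and Methods make them secondary. Procedures and Statistical Analyses also add VLDL-C to the lipid list. These are labelling differences and do not show that more outcomes are primary.

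The defence does not answer the responder point. A between-arm test of mean TG change does not tell the reader how many of the treated-arm responders would have met the rule without the drug.

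**Conclusion.** The concern holds in this limited form: TG is the anchor of the aims but not the stated deciding test, months 2 and 4 are unranked, the governing analysis is unnamed, and the responder percentage lacks a control comparison.

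The multiplicity effect is modest: about 3% rising to 5-8% at month 2, for percent-change tests only. Its direction matters more than its size, since about half to two-thirds of the false favourable results would involve no favourable TG result. The responder gap is the more concrete problem, because about 2-4 of 20 treated participants could be counted as showing drug efficacy by chance. All these figures rest on assumed SDs and correlations. The textual inconsistency does not. This should be corrected, but it does not undermine the trial.

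**What to change.** **Change Goals and Objectives, Methods and Statistical Analyses together.**

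1. Name one primary test at two-sided 0.05: the treatment v control difference (group effect) in percent change in TG from baseline to month 2. Include all randomised participants with a month-2 value, and report the number missing by arm. This comparison is close to one already listed and precedes the removal of non-responders.
2. State that the TG repeated-measures ANOVA is supportive.
3. For Aim 1, report the proportion with a ≥25% TG reduction at month 2 in each arm, with the difference and 95% CI. Methods has all participants attending monthly visits and Table 2 schedules lipids at month 2, so the control data will exist.
4. Label HDL-C, LDL-C, total cholesterol, VLDL-C, the ratios, glucose and insulin secondary or exploratory, reported as estimates with 95% CIs.
5. Reword Primary Aim 2 so that month-4 TG is secondary. Alternatively, place it second in a fixed sequence, but only if its analysis deals with the removal of treated non-responders.

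**Cost.** Wording only; no new visits, samples or participants. An isolated HDL-C, LDL-C or total cholesterol result loses primary status, as does month-4 TG unless it is kept in sequence. The trial then rests on one test with 83-98% power for a 41-point difference but only 43-70% for a 25-point difference (assumed SD 25-35 points). The responder difference will be imprecise and should be presented as an estimate.
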